5.4 Packaging and labelling

Gene-modified fibroblasts are thawed, washed, counted and then packed into syringes capped with luer-screw. A total of 3 labelled syringes containing gene-modified autologous fibroblasts are then put into a petri dish, and sealed with clinical tape. Both syringes and petri dishes are clearly labelled with the study ID and IMP information. The product is finally placed into a medical cooler bag to maintain the product at ambient temperature.

5.5 Distribution and shipment

The IMP will be transported from the Cellular Therapies at GOSH to the trial site – clinical research facility at [name] by a specialised courier at the ambient temperature with a temperature monitor within 8 hrs of the IMP release.

5.6 Storage, dispensing and return of the IMP

Cultured transduced autologous fibroblasts are cryopreserved and store in a liquid nitrogen vessel with vapour phase. On the day of therapy, frozen cells will be removed from liquid nitrogen and quickly thawed in the Cellular Therapies at ICH/GOSH. Thawed cells are recovered and counted. After counting, cells are re-pelleted, and resuspended in 0.9% saline with an approximate concentration of $2-4 \times 10^6$ viable cells/ml. 0.25ml cell suspensions containing approximately $0.8-1.2 \times 10^6$ viable cells are packed into syringes capped with luer-screw. There will be three syringes of transduced cells provided. All syringes are clearly labelled with patient specific identifiers and IMP information and put into a transfer container for transport.

A Proof of Receipt form will be completed to confirm receipt of the product and faxed back to the sponsor and manufacturer. A copy of the form will be filed in the Investigator Site File. If it is found that the packaging has been tampered with or is

damaged, the sponsor will be notified immediately. The product(s) affected will not be used. Each dispensing will be recorded on the IMP Accountability Record. Any unused IMP may be returned to GOSH and stored for research use only.

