	
2. Past medical history of biopsy proven skin malignancy.
 
3. Subjects who have received immunotherapy including oral corticosteroids (Prednisolone >1mg/kg) for more than one week (intranasal and topical preparations are permitted) or chemotherapy within 60 days of enrolment into this study.
 
4. Known allergy to any of the constituents of the investigational medicinal product (IMP).
 
5. Subjects with BOTH:
 
 positive serum antibodies to C7 confirmed by ELISA and positive IIF with binding to the base of salt split skin. 
6. Subjects with positive results for HIV, Hepatitis B, Hepatitis C, HTLV or Syphilis.
 
7. Subjects who are pregnant or of child-bearing potential who are neither abstinent nor practising an acceptable means of contraception when this is in line with the usual and preferred lifestyle of the subject, as determined by the Investigator, for 12 months after the cell injections.

IMP, dosage and route of administration	
IMP: SIN LV-mediated ex vivo transduced autologous fibroblasts expressing codon-optimised COL7A1.
 
DOSAGE: 0.8–1.2 million cells suspended in 0.25ml of 0.9% saline per injection over 1 cm² of intact skin (3 injections of IMP at a single timepoint).
 
ROUTE OF ADMINISTRATION: Intradermal injections.

Active comparator product (Control)	None.
Maximum duration of study participation	32 months (each patient will be followed up for a total of 12 months post-IMP injections and screening will take place up to 4 months prior to the intervention).
Version and date of protocol	Version 4.0, 01/MAR/2016

2. Glossary of Terms

AE	Adverse Event
AR	Adverse Reaction
ATMP	Advanced Therapy Medicinal Product
BEBSS	Birmingham Epidermolysis Bullosa Severity Score
C7	Type VII Collagen
CRF	Case Report Form
DEB	Dystrophic Epidermolysis Bullosa
DEJ	Dermal-Epidermal Junction
DIF	Direct Immunofluorescence
DMC	Data Monitoring Committee
DMEM	Dulbecco's Modified Eagle Medium
DMSO	Dimethyl sulphoxide
EB	Epidermolysis Bullosa
EBS	Epidermolysis Bullosa Simplex
EDTA	Ethylenediaminetetraacetic acid
EUD	European Union Directives
FACS	Fluorescence activated cell sorting
FCS	Fetal calf serum
GCP	Good Clinical Practice
GMP	Good Manufacturing Practice
GOSH	Great Ormond Street Hospital
GSTT	Guy's and St Thomas' NHS Foundation Trust
GTAC	Gene Therapy Advisory Committee
GvHD	Graft versus Host Disease
HIV	Human immunodeficiency virus
HLA	Human Leucocyte Antigen

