5.1 Investigational Medicinal Product

The patient specific gene-modified autologous fibroblasts are classified as an Investigational Medicinal Product (IMP) that comes under the European Union Directives (EUDs) on medicinal products and are subject to advanced therapy medicinal product (ATMP) guidelines and will be manufactured and expanded according to GMP regulations. Each participant will be screened for infectious diseases in accordance with the EU directive 2006/17 (Commission Directive 2006/17/EC of 8 February 2006) prior to skin biopsy for cell culture to produce autologous fibroblasts under GMP conditions. The pCCL-PGK-COL7 lentiviral vector gene modified autologous fibroblasts which are suspended in saline will be produced under MIA(IMP) 17328 at Cellular Therapies, Great Ormond Street Hospital for Children NHS Foundation Trust (GOSH), [name]. The IMP manufacturing site is non-commercial and part of an academic institution with a certified manufacturer/ importer's licence as well as GMP and QP certification. The unit also has a HTA licence and JACIE accreditation for transplantation.

Release of the IMP will require qualified person (QP) examination of the manufacturing record, liquid nitrogen temperature monitor recorder and other tests undertaken on cells to confirm transduction (copy number). Assays for information include evidence of reconstitution of C7 expression by flow cytometry, immunostaining and immunoblot (**Table 1**).

If the genetically modified autologous RDEB primary fibroblasts do not meet specification, the transduced cells will not be released. Efficacy and safety assessments will be carried out and data will be recorded in the Case Report Forms (CRFs).

LENTICOL-F Version 4.0, 01/MAR/2016

EudraCT Number: 2014-004884-19

Test	Day/week during manufacturing	Specification
BACTalert	Weekly	No organisms detected
Cell number	Before release	2.4-3.6X10 ⁶ viable cells for gene modified fibroblasts
Stable lentiviral transduction	specific qPCR	Copy number = 0.01-1.0 copy/cell
C7 protein expression*	Flow cytometry, immunostaining and immunoblot	restoration of C7 expression compared to baseline C7
Cell storage temperature	Daily record	Less or equal to -70°C

**depending on the mutation, some subjects may have residual protein expression*

Table 1: Specification for releasing transduced RDEB autologous fibroblasts.

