5.2 Dosing regimen

Each trial participant will receive three intradermal injections of gene-modified autologous fibroblasts on Day 0. Each 1cm² of intact skin will be injected with 0.8–1.2x10⁶ cells/ 0.25ml of normal saline. Once all 3 syringes are received, they will be injected as described in Section 5.7. The person handling and injecting the IMP will have appropriate training. Trial subjects will be monitored closely for any immediate allergic reactions and their vitals monitored every 15mins for half an hour. Vital signs will include blood pressure, respiratory rate, heart rate, pulse oximetry and temperature.

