5.7 IMP administration

The selected area of intact skin of each trial participant will be marked with an ink tattoo marker that is normally used for to mark the sites of radiotherapy on cancer patients. No radiotherapy or irradiation will be involved here. The schema of the tattoo sites may vary depending on the individuals but the investigator will aim to provide the minimal number of tattoos required in order to aid the accurate identification of the injection sites at future visits. Prior to injections, the intact skin will be cleaned with Chlorhexidine solution and the IMP administered by the trained investigator. Each injection of the IMP containing $0.8\text{--}1.2 \times 10^6$ cells suspended in 0.25ml of 0.9% saline, will be administered intradermally into 1cm^2 area of intact skin (x3). Trial subjects will be monitored closely for any immediate allergic reactions and their vitals monitored every 15mins for half an hour.

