2.3 Treatment delivery

The number of patients who receive treatment will be reported (appendix - table 2).

Treatment related characteristics such as site of treatment and cell numbers injected will be summarised for each patient (appendix - table 5).

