¹Type of RDEB: *GS=Generalised severe, GI=Generalised intermediate, In=Inversa, Lo=Localised, PT=Pretibial, Pru=Pruriginosa, Cen=Centripetalis, BDNB=Bullous dermolysis of the new born.*

²*C7 IF microscopy: CD=Complete deficiency, PD=Partial deficiency, ND=No deficiency.*

³*C7 MII ± SE = Type VII collagen mean immunofluorescence intensity ± standard error*

⁴*AF ± SE = anchoring fibrils ± standard error*

Note: All baseline values are taken from visits 1A or 1B which are up to 6 months and 6 weeks prior to administration of IMP, respectively. With the exception of the ELISPOT values which are taken at visit 2 prior to administration of the IMP.

Table 5: Treatment related data per patient

Patient ID	Time from treatment of previous patient (days)	Date of treatment	Site of treatment	Cell numbers injected in Square 1 (x10 ⁶ cells in 0.25ml of 0.9% saline)	Cell numbers injected in Square 2 (x10 ⁶ cells in 0.25ml of 0.9% saline)	Cell numbers injected in Square 3 (x10 ⁶ cells in 0.25ml of 0.9% saline)
001	xx	dd/mm/yyyy		xx.x	xx.x	xx.x
002						
003						
004						
005						
006						
007						
008						
009						
010						

Table 6: Summary of adverse events and reactions, including SAEs

		Number of events nAE	Number of patients n
Overall			
Adverse events (AE)		xx	xx
Serious adverse events (SAE)		xx	xx
Suspected unexpected serious adverse reactions (SUSAR)		xx	xx
Serious adverse reactions (SAR)		xx	xx
Severity Grade¹			
1		xx	xx
2		xx	xx
3		xx	xx
4		xx	xx
5		xx	xx

NOTE: nAE = number of adverse events (or SAE/SUSAR/SAR); n =number of patients experiencing at least one event.

¹ **Severity grade:** 1=mild: awareness of signs or symptoms, but easily tolerated; 2=moderate: uncomfortable enough to cause interference with usual activity; 3=severe: incapacity with inability to work or do usual activity; 4=life-threatening; 5=death.

Table 7: Adverse events and reactions, including SAEs, per patient

Patient ID	Event	Days from treatment to onset	Start date dd/mm/yyyy	End date dd/mm/yyyy	Serious? ¹ Y/N	Severity Grade ² (1-5)	Causality ³	Outcome ⁴	Treatment (free text)	Medications received if any

¹**Serious:** yes/no. *NOTE: If yes, qualifies an AE/R as Serious (SAE/R)*

²**Severity grade:** 1=mild: awareness of signs or symptoms, but easily tolerated; 2=moderate: uncomfortable enough to cause interference with usual activity; 3=severe: incapacity with inability to work or do usual activity; 4=life-threatening; 5=death;

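### The resuspension concentration in Protocol 5.6 (about 2–4 million viable cells/ml) does not deliver the stated dose of 0.8–1.2 million cells in 0.25 ml, which needs 3.2–4.8 million/ml

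*Protocol*

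**What the plan says.** Protocol 5.6 describes preparation on the day of therapy. Frozen cells are thawed, counted, pelleted again and resuspended in saline at "an approximate concentration of $2-4 \times 10^6$ viable cells/ml. 0.25ml cell suspensions containing approximately $0.8-1.2 \times 10^6$ viable cells are packed" into three syringes.

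The dose appears in several other places, always with the same numbers:

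- Protocol synopsis: "0.8–1.2 million cells suspended in 0.25ml of 0.9% saline per injection".
- Protocol 5.2: "Each 1cm² of intact skin will be injected with 0.8–1.2x10⁶ cells/ 0.25ml of normal saline".
- Protocol 5.7 repeats it for administration: 0.8–1.2 million "cells suspended in 0.25ml of 0.9% saline, will be administered intradermally into" 1 cm² of intact skin, three times.
- Protocol 4.2 and SAP 1.2 and 1.5 give the same dose and volume.

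Protocol 5.3 and 9.1 also give 0.25 ml as the volume per syringe and per site. Table 1 in Protocol 5.1 sets the cell number for release at 2.4–3.6 million "viable cells for gene modified fibroblasts". The 2–4 million/ml concentration appears only in 5.6.

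**The concern.** Two adjacent sentences in 5.6 give a concentration and a syringe content that should be linked by one multiplication, and they are not. The section describes how a patient-specific gene therapy product is made up, in a phase 1 trial with a single dose range given once.

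If staff worked to the printed concentration, most of its range would under-fill the syringes against the protocol minimum. The three-syringe total would then also fall below the release minimum, on the day the patient is due to be treated.

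**Working it through.** **Inputs**

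- Concentration: about 2–4 million viable cells/ml (Protocol 5.6).
- Volume per syringe: 0.25 ml (Protocol synopsis, 4.2, 5.2, 5.3, 5.6, 5.7, 9.1; SAP 1.2, 1.5).
- Cells per syringe: about 0.8–1.2 million (the same places, except Protocol 5.3 and 9.1, which give the volume only).
- Number of syringes: 3 (Protocol 5.2, 5.4, 5.6).
- Release total: 2.4–3.6 million viable cells (Protocol 5.1, Table 1).

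**Step 1. Try to reproduce the stated syringe content.** Cells per syringe = concentration × volume.

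| Concentration (million/ml) | Cells per syringe (million) | Three syringes (million) | Against minimum of 0.8 per syringe and 2.4 in total |
|---|---|---|---|
| 2.0 | 2.0 × 0.25 = 0.50 | 1.50 | 37.5% short |
| 3.0 (midpoint) | 3.0 × 0.25 = 0.75 | 2.25 | 6.25% short |
| 3.2 | 3.2 × 0.25 = 0.80 | 2.40 | exactly at minimum |
| 4.0 | 4.0 × 0.25 = 1.00 | 3.00 | within range |

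The printed concentration gives 0.5–1.0 million cells per syringe, so the stated 0.8–1.2 million is not reproduced. The shortfalls are (0.8 − 0.5)/0.8 = 37.5% and (0.8 − 0.75)/0.8 = 6.25%.

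**Step 2. Concentration the dose needs.** Dose ÷ volume: 0.8/0.25 = 3.2 and 1.2/0.25 = 4.8, so 3.2–4.8 million/ml.

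**Step 3. Overlap.** The range 2–4 meets 3.2–4.8 only at 3.2–4.0 million/ml. The part of the printed range that under-fills is (3.2 − 2.0)/(4.0 − 2.0) = 60%. The part of the dose range out of reach is everything above 1.0 million: (1.2 − 1.0)/(1.2 − 0.8) = 50%.

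**Step 4. Which figure is out of line.** Three syringes of 0.8–1.2 million make 2.4–3.6 million, which is exactly the Table 1 total. Over 3 × 0.25 = 0.75 ml, that total is 2.4/0.75 = 3.2 to 3.6/0.75 = 4.8 million/ml. Dose, volume, syringe count and release total are consistent with one another; only the 5.6 concentration is not.

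**Step 5. Other readings.**

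- *A different fill volume.* The minimum dose at 2 million/ml would need 0.8/2 = 0.40 ml, and the maximum at 4 million/ml would need 1.2/4 = 0.30 ml. No single volume fits both ends, and 0.25 ml is given throughout.
- *Loss on thawing.* Both figures in 5.6 are for viable cells after thawing and counting, and no later concentrating step is described.
- *Rounding.* The difference between 2 and 3.2 is too large to be rounding.

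**The case against.** The strongest reply is that the 5.6 concentration does not set the dose. It is labelled approximate and describes an intermediate handling step. The next sentence states what each syringe must hold, and the printed range does include compliant concentrations (3.2–4.0 million/ml), which give 0.8–1.0 million cells. Not reaching the upper half of the dose range is no deviation, because any dose from 0.8 million upwards within the range complies.

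There are also safeguards. Protocol 5.1 says that if specification is not met "the transduced cells will not be released". SAP 2.3 plans that "Treatment related characteristics such as site of treatment and cell numbers injected will be summarised for each patient", and SAP Table 5 has a column for each site, the first headed "Cell numbers injected in Square 1". Protocol 5.3 refers to the manufacturing dossier for the full procedures, and that dossier may hold the governing figure.

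Most of this stands, and it limits the weight of the point. The Table 1 total is also probably the same dose multiplied by three, so it shows consistency but is not separate evidence. The percentages describe the printed range and say nothing about how often a syringe would actually be under-filled.

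None of it reconciles the two sentences in 5.6. The release check would stop an under-filled product, but it also shows the conflict: a batch made up at 2 or 3 million/ml and filled as described would fall below the protocol's own release minimum.

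**Conclusion.** The inconsistency is real and the point holds, as a minor one. As printed, the concentration yields 0.5–1.0 million cells per syringe against a stated 0.8–1.2 million. It under-fills over the lower 60% of its range, by up to 37.5% of the minimum dose. The intended dose is not in doubt.

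This rests on two assumptions: that syringes are filled directly from the suspension described in 5.6, and that the Table 1 total refers to the contents of the three syringes, which the exact factor of three supports. That the concentration, and not the dose, is the figure to correct follows from the agreement of everything else in the two documents; the dossier should confirm it.

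The trial's conclusions are unaffected. The primary outcome is adverse events, no hypothesis tests are planned, and the sample-size reasoning does not use the cell dose.

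**What to change.** In Protocol 5.6, change the concentration to about 3.2–4.8 million viable cells/ml, after checking it against the manufacturing dossier. Then 0.25 ml holds 3.2 × 0.25 = 0.8 to 4.8 × 0.25 = 1.2 million cells, and three syringes hold 2.4–3.6 million, matching both the dose and Table 1.

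The cost is one corrected figure and one check against an existing document. The dose, Table 1 and the SAP stay as they are, and no new tests, data or analyses are needed.

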5.7 IMP administration

The selected area of intact skin of each trial participant will be marked with an ink tattoo marker that is normally used for to mark the sites of radiotherapy on cancer patients. No radiotherapy or irradiation will be involved here. The schema of the tattoo sites may vary depending on the individuals but the investigator will aim to provide the minimal number of tattoos required in order to aid the accurate identification of the injection sites at future visits. Prior to injections, the intact skin will be cleaned with Chlorhexidine solution and the IMP administered by the trained investigator. Each injection of the IMP containing $0.8\text{--}1.2 \times 10^6$ cells suspended in 0.25ml of 0.9% saline, will be administered intradermally into 1cm^2 area of intact skin (x3). Trial subjects will be monitored closely for any immediate allergic reactions and their vitals monitored every 15mins for half an hour.

5.8 Drug accountability

Each IMP dispensing will be documented on the IMP accountability form, along with unused returned study treatments. The study monitor will check all dispensing against the study schedule and record all administrations to the trial participants. A full review of the actual dispensed, administered and returned study treatments will be performed.

[figure not shown]

Figure 18: Map showing the sites of IMP injection and the timeline of the biopsies to be taken.

5.9 Subject compliance

The IMP will be administered to the trial participants attending St John's Institute of Dermatology at GSTT in the designated Clinical Research Facilities, [name]. Non compliance issues are not expected as the treatment is administered in hospital setting by a member of the research team. Skin biopsies and blood tests will also be performed by a member or members of the clinical team. However, because the study population involves adults with a severe blistering skin disease, if a blood test is unobtainable at a particular time, the investigators may use a blood sample obtained at a more convenient time (but chronologically related). Participants will be assessed for any adverse events and concomitant medications at each visit from V1B but otherwise, no assessments are scheduled to be performed by study subjects

at home so no subject compliance issues are expected. Support and guidance will be provided by members of the clinical research team as required.

5.10 Concomitant medication

For management of concomitant therapies, please refer to the Investigators Brochure (IB). The study subjects can continue to receive their regular medication(s). A complete listing of all concomitant medication received during the treatment phase will be recorded in the relevant CRF.

6 Selection and withdrawal of subjects

6.1 Inclusion criteria

- I. Clinical and genetic diagnosis of RDEB with confirmed bi-allelic *COL7A1* mutations.
- II. A reduced number or morphologically abnormal anchoring fibrils confirmed by TEM.
- III. At least 5x3cm of intact skin on the trunk and/or extremities that is suitable for cell injections.
- IV. Able to undergo local anaesthesia.
- V. Subjects aged ≥ 17 years and able to give informed consent prior to the first study intervention.

6.2 Exclusion criteria

- I. Subjects who received other investigational medicinal products within 6 months prior to enrolment into this study.
- II. Past medical history of biopsy proven skin malignancy.
- III. Subjects who have received immunotherapy including oral corticosteroids (Prednisolone >1 mg/kg) for more than one week (intranasal and topical preparations are permitted) or chemotherapy within 60 days of enrolment into this study.
- IV. Known allergy to any of the constituents of the investigational medicinal product (IMP).
- V. Subjects with **BOTH**:
 - positive serum antibodies to C7 confirmed by ELISA **and**
 - positive IIF with binding to the base of salt split skin.
- VI. Subjects with positive results for HIV, Hepatitis B, Hepatitis C, HTLV or Syphilis.

VII. Subjects who are pregnant or of child-bearing potential who are neither abstinent nor practising an acceptable means of contraception when this is in line with the usual and preferred lifestyle of the subject, as determined by the Investigator, for 12 months after the cell injections.

6.3 Selection of participants

The patient population is under the care of the specialist EB team at St John's Institute of Dermatology, GSTT. As a tertiary care centre, patients may have been referred from other regional district hospitals in the first instance. Potential study subjects will be identified from the National EB database that includes patients from both GSTT and nationally and an initial approach made by members of the clinical team. Potential participants may also be recruited from Patient Identification Centres. Study information sheets will be provided and individuals interested will be invited for further consultation and screening, assessed for eligibility, and consented as necessary. All individuals invited to participate in the study will have a minimum of 24 hours to make their decision.

6.4 Randomisation procedure / code break

This is a phase 1, non-randomised, open-label, single-centre, proof-of-concept study, therefore randomisation procedure/code break is not applicable.

6.5 Withdrawal of subjects

Participants have the right to withdraw from the study at any time for any reason. The investigator also has the right to withdraw patients from the study drug in the event of inter-current illness, AEs, SAEs, SUSARs, protocol violations, cure, administrative reasons or other reasons. It is understood by all concerned that an excessive rate of withdrawals can render the study un-interpretable, therefore unnecessary withdrawal of patients should be avoided. Should a patient decide to withdraw from the study, all efforts will be made to report the reason for withdrawal as thoroughly as possible.

Should a participant withdraw from the study after the injection of the IMP, efforts will be made to continue to obtain follow-up data, with the permission of the participant. If a participant withdraw before the IMP injection, the participant will be replaced.

